8.2.3.1.6. Adverse reactions in patients excluded from the safety analysis set

Among CRF-collected patients, a listing of adverse reactions will be prepared for patients excluded from the safety analysis set. In addition, patients with an adverse reaction will be summarized by SOC and PT.

8.2.3.2. Adverse events

8.2.3.2.1. Adverse events by serious/non-serious

The number and proportion of patients with serious adverse events will be summarized by SOC and PT. Non-serious adverse events will also be tabulated in the same manner, but the threshold for the incidence will be set as necessary, and only events with the incidence at or above the threshold will be tabulated. This analysis will be performed only for the consented safety analysis set.

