#### 9.2. Patient consent

As this study does not involve data subject to privacy laws according to applicable legal requirements, or it is an information provision based on the law (even though that involve data subject to privacy laws according to applicable legal requirements), obtaining informed consent from patients by Pfizer is not required with regard to the personal information provision from the study site to Pfizer. Also, because the report of information or results collected in this study to the local regulatory authority or healthcare providers by Pfizer as needed is an information provision based on the law, obtaining informed consent from patients by Pfizer is not required.

In this study, Pfizer will collect information that cannot identify specific patients from the institutions. The results of this study, which are prepared not to identify specific patients, may be reported to Pfizer Inc., which is the corporate parent of the sponsor of this study, or group companies, or regulatory authorities in other countries, as needed, or published it as a presentation at academic conferences or manuscript for the purpose of providing proper use information for this drug. If these information falls under personal information of the Personal Information Protection Act, these actions may not be based on the laws or regulations, and therefore, may correspond to provision to the third party and using the

information for purposes other than business that require consent from the patient. Therefore, the study institutions will obtain written or verbal consent from the patients to be included in this study so that Pfizer can use the results of this study to report to Pfizer Inc., group companies or regulatory authorities in other countries, or to present it at academic conferences or publish manuscript, etc. Whether consent is obtained from patients or not is described in the CRF. The original of the written informed consent form should be retained by the study investigator.

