5.3. Other Analysis Sets

5.3.1. Consented Safety Analysis Set

Analysis set limited to patients who gave consent among the safety analysis set

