8.2. Statistical Analyses

Analyses in the safety analysis set and the efficacy analysis set will also be performed in the consented safety analysis set and the consented efficacy analysis set, but the details will be separately specified. At the time of analysis, the safety analysis set and the efficacy analysis set will be replaced with the consented safety analysis set and the consented efficacy analysis set, respectively.

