8.2.3. Safety analysis

Refer to Section 6.1 for the evaluation period for adverse reactions and adverse events. The listing will include all events reported in this study.

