8.2.3.1.2. Serious adverse reactions

Serious adverse reactions will be summarized by SOC and PT in terms of number and proportion.

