8.2.4.5. Death from any cause

Deaths from any cause will be analyzed in Efficacy Analysis Sets 1, 2, and 3 as described in Section 8.1.4.

The frequency and proportion of events and censoring will be calculated separately. The period at risk of events is defined as the number of days from the start date of treatment to the onset date of event, date of last observation, or Day 28 after the end of treatment, whichever comes first, and the mean will be calculated.

For the number of days from the start date of treatment to the onset date of event, frequency and its proportion will be calculated and shown in a figure.

8.2.4.6. Hospitalization for treatment of infection caused by SARS-CoV-2 or death from any cause

Hospitalization for treatment of infection caused by SARS-CoV-2 or death from any cause will be analyzed in Efficacy Analysis Sets 2 and 3 in accordance with Section 8.1.4.

The frequency and proportion of events and censoring will be calculated separately. Events will be tabulated not only for hospitalization or death but also for each. The period at risk of events is defined as the number of days from the start date of treatment to the onset date of event, date of last observation, or Day 28 after the end of treatment, whichever comes first, and the mean will be calculated.

For the number of days from the start date of treatment to the onset date of event, frequency and its proportion will be calculated and shown in a figure.

For patients who developed events, the following patient characteristics will be tabulated according to Section 8.1.

- Age
- Number of risk factors for aggravation of infection caused by SARS-CoV-2 [absent, 1, 2, 3, 4, number unknown, unknown] * If the number of applicable risk factors is unknown, "number unknown" should be selected. If it is not known that there are risk factors, the patient will be classified as "unknown."
- Number of SARS-CoV-2 vaccination doses (vaccination on or before the day before the start of administration of this drug) [none, 1, 2, 3, 4 or more, unknown]

As a sensitivity analysis, the above analysis will be performed by changing the definition to the event definition of hospitalization shown in Section 6.2.

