9. LISTINGS

The following listings will be prepared:

- Patient listing
- List of patients with adverse events
- List of patients with adverse reactions
- List of patients with adverse reactions excluded from safety analysis
- List of patients with excluded adverse reactions included in safety analysis
- List of patients with adverse reactions among contraindicated patients
- List of patients with serious adverse reactions

- List of patients with serious adverse events
- List of deaths
- List of efficacy evaluation
- List of complications corresponding to risk factors for aggravation of infection caused by SARS-CoV-
- List of concomitant drug therapies for infection caused by SARS-CoV-2
- List of concomitant non-drug therapies for infection caused by SARS-CoV-2
- List of SARS-CoV-2 viral tests
- List of body temperature and percutaneous arterial oxygen saturation (SpO₂)

In addition, forms necessary for re-examination application (PSEHB/PED Notification No. 0325-10 dated March 25, 2020 issued by the Director of Pharmaceutical Evaluation Division, Pharmaceutical Safety and Environmental Health Bureau, Ministry of Health, Labour and Welfare) will be prepared.

Furthermore, forms necessary for periodic safety reports (PSEHB/PED Notification No. 1128-5 dated November 28, 2017 issued jointly by the Director of Pharmaceutical Evaluation Division and the Director of Pharmaceutical Safety Division, Pharmaceutical Safety and Environmental Health Bureau, Ministry of Health, Labour and Welfare) will be prepared.

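### The only visible SOC/PT table of all-cause serious adverse events is limited to consenting patients; it should also be run in the full safety analysis set

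*SAP*

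**What the plan says.** SAP 8.2.3.2.1 tabulates patients with serious adverse events, as number and proportion by SOC and PT. Non-serious events are handled the same way, above an incidence threshold to be set as needed. The section closes: "This analysis will be performed only for the consented safety analysis set". SAP 5.3.1 defines that set: "Analysis set limited to patients who gave consent among the safety analysis set".

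The general rule in SAP 8.2 is different: "Analyses in the safety analysis set and the efficacy analysis set will also be performed in the consented safety analysis set". Consented-set results are there an addition to the full-set results.

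For the full safety analysis set, SAP 8.2.3.1.2 says: "Serious adverse reactions will be summarized by SOC and PT in terms of number and proportion". SAP 6.1 defines adverse reactions as events the treating physician considered related, and adverse events as all-causality. SAP 8.2.3 adds "The listing will include all events reported in this study", and SAP 9 includes a "List of patients with serious adverse events".

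On consent, protocol 9.2 says that giving results to the local regulatory authority or to healthcare providers "is an information provision based on the law, obtaining informed consent from patients by Pfizer is not required". Consent is sought for reporting to the parent and group companies, for overseas authorities, and for presentation or publication.

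**The concern.** The objective in protocol 7 is safety in patients receiving the drug, and the target of 3000 in protocol 8.5.1 is set for the safety analysis set. Neither is confined to patients who agree to publication or overseas reporting.

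An all-cause serious-event proportion complements the adverse-reaction tables because it does not depend on the individual causality judgement. That judgement is harder in a study without a control group, a limitation that protocol 8.9 acknowledges. If the all-cause proportion exists only for consenting patients, it describes a subset whose membership may be related to outcome. Protocol 8.2.1 allows enrolment of patients who started the drug before the site contract was concluded, so for some of them the outcome may already be known when consent is sought. The documents do not show in which direction any selection would act. The smaller denominator also costs some precision.

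**Working it through.** **1. Which outputs cover which events and patients**

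| Output | Events | Patients |
|---|---|---|
| SAP 8.2.3.1.1 to 8.2.3.1.3, SOC/PT tables | Adverse reactions | Safety analysis set |
| SAP 8.2.3.1.5, safety specifications | Selected events, under the adverse-reactions heading | Safety analysis set |
| SAP 8.2.3.1.6, SOC/PT | Adverse reactions | Patients excluded from the safety analysis set |
| SAP 8.2.3.3, subgroups | Adverse reactions | Safety analysis set |
| SAP 8.2.3.2.1, SOC/PT tables | All-cause, serious and non-serious | Consented safety analysis set only |
| SAP 9, listings | All-cause | No consent limit stated |
| SAP 8.2.4.5 and 8.2.4.6 | Death; COVID-19 hospitalization or death | Efficacy analysis sets |

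The cell for an all-cause serious-event proportion by SOC/PT in the full safety analysis set is empty. The revision history for SAP Version 3 shows that the consented sets were added, the table of all adverse events was deleted and the serious/non-serious method was changed in the same version. The restriction therefore looks deliberate, but the visible text gives no reason for it.

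**2. The plan's own sample-size figures**

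Protocol 8.5.2 gives 3000 patients for a 95% chance of at least one case of an unknown reaction at 0.1%. Solving 1 − (1 − 0.001)^n = 0.95 gives n = ln(0.05)/ln(0.999) = 2994.2, so 2995; at n = 3000 the probability is 0.9503. For the 7.8% reaction rate, the binomial probability of at least 214 patients out of 3000 is 0.920, consistent with the stated 90%. Both figures reproduce. They concern adverse reactions, which stay in the full set, so the restriction does not affect them.

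**3. Precision**

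Assumptions: a serious-event rate of 2% and consent of 70% to 100%. The documents give neither. Exact (Clopper-Pearson) 95% intervals, the method named in SAP 8.1.3 for proportions:

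| Consent | Events / patients | 95% interval | Width (points) |
|---|---|---|---|
| 100% | 60/3000 | 1.530–2.567% | 1.037 |
| 95% | 57/2850 | 1.518–2.584% | 1.065 |
| 90% | 54/2700 | 1.506–2.602% | 1.096 |
| 80% | 48/2400 | 1.478–2.643% | 1.165 |
| 70% | 42/2100 | 1.445–2.694% | 1.249 |

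**4. Selection**

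Suppose 60 of 3000 patients truly have a serious event (2.00%). The proportion shown is (60 × consent among cases) / (3000 × overall consent).

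| Overall consent | Consent among cases | Proportion shown |
|---|---|---|
| 80% | 70% | 42/2400 = 1.75% |
| 80% | 90% | 54/2400 = 2.25% |
| 90% | 80% | 48/2700 = 1.78% |
| 90% | 100% | 60/2700 = 2.22% |
| 95% | 85% | 51/2850 = 1.79% |
| 95% | 100% | 60/2850 = 2.11% |

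With equal consent in cases and non-cases, 48/2400 = 54/2700 = 57/2850 = 2.00%, and there is no shift.

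**The case against.** The best defence is that nothing promised is withheld. Protocol 8.7 commits only to adverse-reaction numbers and proportions, and the SAP delivers those in detail in the full set. That stands: this is not a protocol breach.

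Nor are serious events lost. Protocol 10.1 requires every SAE to be reported within 24 hours regardless of causality. The SAP lists all events, and for mortality it says: "Deaths from any cause will be analyzed in Efficacy Analysis Sets 1, 2, and 3 as described in Section 8.1.4". This also stands. A crude proportion could be counted by hand from the listings. However, the death and hospitalization analyses use the efficacy sets and are not by SOC/PT, and a hand count is not a pre-specified table.

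A purpose can be inferred: a consented-only table suits publication and overseas use, which do need consent. That explains why the consented version exists, but not why the full-set version is absent. The regulatory forms named in SAP 9 might hold an equivalent table. Their content is not shown, so this cannot be excluded; if they do, a cross-reference would settle the point.

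The sizes are modest and assumed, and every selection scenario above lies inside the full-set sampling interval of 1.53–2.57%. That limits the weight of the point. But a shift from selection is a bias that a larger sample does not remove, and here it can be avoided at almost no cost. Finally, without a control group an all-cause proportion cannot separate drug from disease. That is true, and it is why the table complements the adverse-reaction tables and does not replace them.

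The restricting sentence could be read as covering only the non-serious table, but under a single heading for both, the plain reading covers both.

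**Conclusion.** The concern holds. As written, the SAP specifies no all-cause serious-event proportion by SOC/PT for the full safety analysis set, while specifying one for the consented subset. The consent provisions do not require this for local regulatory use, and the visible text gives no reason for it. The gap is in a summary table with its denominator, not in data collection or case reporting.

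The effect is modest. Under the assumed 2% rate, the interval width grows by at most 0.21 percentage points (1.249 − 1.037) at 70% consent. Ten-point differences between consent among cases and consent overall move the proportion by about a quarter of a point or less. The shift is zero if consent is unrelated to events, and its direction is unknown. The change is worth making because it removes a possible bias from the serious-event summary for very little work.

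**What to change.** In SAP 8.2.3.2.1, produce the serious adverse event table by SOC and PT in the full safety analysis set for local regulatory reporting, and keep the consented-set version for the uses that need consent under protocol 9.2. Beside the consented-set table, state the number consenting out of the safety analysis set, so that readers can judge how far selection could matter. The non-serious table can stay as planned.

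The cost is one SAP sentence, one further run of an existing table program and one count. Consent status is already recorded in the CRF, so no new data, patients or site work are needed.

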8.2.3.3. Subgroup analyses

The number and proportion of patients who experienced at least 1 adverse reaction will be tabulated by factor specified in Section 5.4. In addition, risk ratios of the incidence of adverse reactions between subgroups will be calculated as described in Section 8.1.3. However, if there is a category with less than 10 patients and it is determined difficult after reconsideration of the classification of categories, the risk ratio for the category will not be calculated. Similar analyses will be performed for adverse reactions with PTs of dysgeusia, taste disorder, diarrhoea, vomiting, nausea, decreased appetite, and rash by each of the following factors.

Descriptions in brackets indicate the levels of subgroups, and the underlined level indicates the standard level for calculation of risk ratio.

- Hepatic impairment [absent, present, unknown]
- Hepatic impairment [absent, mild, moderate, severe, unknown (presence unknown or severity unknown)]
- Renal impairment [absent, present, unknown]
- Renal impairment [absent, mild, moderate, severe, unknown (presence unknown or severity unknown)]
- Age [<15 years, \ge 15 to <65 years, \ge 65 years]
- Age [<18 years, ≥18 years]
- Age [\leq 65 years, \geq 65 to \leq 75 years, \geq 75 years]
- Pregnancy [absent, present] * Female only
- Contraindications for coadministration/precautions for coadministration [both absent, precautions for coadministration present, contraindications for coadministration present] Patients with precautions for coadministration and patients with contraindications for coadministration may overlap. For patients

with precautions for coadministration and patients with contraindications for coadministration, events after the start of coadministration will be included.

 Complicated with HIV infection and concomitantly using anti-HIV therapy including ritonavir or cobicistat [absent, present] * Specifically, patients concomitantly using ritonavir or cobicistat will be classified as present and other patients as absent.

Adverse reactions will be summarized in terms of number and proportion by each of the following factors among the factors specified in Section 5.4 for each SOC and PT.

- Hepatic impairment [absent, present]
- Hepatic impairment [absent, mild, moderate, severe]
- Renal impairment [absent, present]
- Renal impairment [absent, mild, moderate, severe]
- Age [<15 years, \ge 15 to <65 years, \ge 65 years]
- Age [<18 years, \ge 18 years]
- Age [<65 years, ≥65 to <75 years, ≥75 years]
- Pregnancy [absent, present] * Female only
- Contraindications for coadministration/precautions for coadministration [both absent, precautions for coadministration present, contraindications for coadministration present] Patients with precautions for coadministration and patients with contraindications for coadministration may overlap. For patients with precautions for coadministration and patients with contraindications for coadministration, events after the start of coadministration will be included.
- Complicated with HIV infection and concomitantly using anti-HIV therapy including ritonavir or cobicistat [absent, present] * Specifically, patients concomitantly using ritonavir or cobicistat will be classified as present and other patients as absent.

A listing of adverse reactions will be prepared for contraindicated patients.

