# 13. ADDITIONAL MEASURES THAT MAY BE IMPLEMENTED BASED ON THE STUDY RESULTS AND CRITERIA FOR DETERMINATION OF THE INITIATION

Review the risk management plan including the following contents at the scheduled timing of milestones.

- 1. Review the necessity for changing the contents of risk minimization activities for the current safety specifications.
- 2. Review the necessity for changing the contents of this study plan including the presence or absence of new safety specifications (continuation of the study, implementation of additional study, etc.).

3. Review the necessity for formulating risk minimization measures for new safety specifications.

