6. ENDPOINTS AND COVARIATES

6.1. Safety Endpoints

The safety evaluation period is defined as the observation period in Section 2.2. The number of days from the start date of treatment to the onset date of event will be calculated as [event onset date – start date of treatment with this drug + 1].

- Adverse reactions: Adverse events for which the causal relationship was considered as related by the treating physician
- Adverse events: All-causality adverse events
- Serious adverse events or serious adverse reactions: Adverse events or adverse reactions considered by the treating physician to be serious
- Events to be handled as safety specifications are specified separately.

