8.2.3.1.5. Safety specifications

For the following safety specifications, patients who experienced relevant events will be summarized in terms of number and proportion:

- Toxic epidermal necrolysis/oculomucocutaneous syndrome
- Hepatic impairment
- Hyperglycemia/diabetes mellitus
- Bleeding tendency

In addition, patients who experienced each safety specification will be summarized by action taken and outcome for each SOC and PT.

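### SAP 8.2.3.3 breaks the safety specifications down by subgroup only as separate SOC and PT rows, with no grouped per-patient count or risk ratio

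*SAP*

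**What the plan says.** Protocol 7.1 names five risks. Three are identified: toxic epidermal necrolysis/oculomucocutaneous syndrome, hepatic function disorder and anaphylaxis. Two are potential: hyperglycemia/diabetes mellitus and bleeding tendencies. SAP 6.1 places their definitions elsewhere: "Events to be handled as safety specifications are specified separately".

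SAP 8.2.3.1.5 plans the grouped analysis: "For the following safety specifications, patients who experienced relevant events will be summarized in terms of number and proportion". It lists four of the five risks, without anaphylaxis. The only further breakdown is by action taken and outcome, for each SOC and PT.

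SAP 8.2.3.3 has three layers of subgroup analysis:

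1. Any reaction, with risk ratios: "The number and proportion of patients who experienced at least 1 adverse reaction will be tabulated by factor specified in Section 5.4".
2. Seven single terms, analysed the same way: "Similar analyses will be performed for adverse reactions with PTs of dysgeusia, taste disorder, diarrhoea, vomiting, nausea, decreased appetite, and rash".
3. All adverse reactions as number and proportion, "by each of the following factors among the factors specified in Section 5.4 for each SOC and PT". The factors include hepatic and renal impairment, age, pregnancy, HIV therapy and "Contraindications for coadministration/precautions for coadministration [both absent, precautions for coadministration present, contraindications for coadministration present". No risk ratio is specified here, and the hepatic and renal factors drop the unknown level used in layer 2.

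The same section adds a listing of adverse reactions in contraindicated patients. SAP 9 adds patient and adverse-reaction listings. SAP 8.2.3.4 allows further analyses but commits to none.

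**The concern.** The named risks get less subgroup analysis than taste disturbance or nausea, although the factors most naturally paired with them, hepatic impairment and interacting drugs, are already in the plan. Protocol 13 says that at each milestone the sponsor will "Review the necessity for changing the contents of risk minimization activities for the current safety specifications". A reader of the results may then want to know how many liver-impaired patients had a hepatic reaction, or how many patients on an interacting drug bled. No planned table gives that number as one count of distinct patients with an interval or ratio.

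The remaining planned views are coarser or finer than the question. Any reaction mixes the specification with all other reactions. PT rows split it, and an SOC row matches it only if the terms of the two coincide.

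**Working it through.** **Plan's own figures.** Inputs are N = 3000 and 7.8% (Protocol 8.5, SAP 2.2).

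- Expected patients with a reaction: 3000 × 0.078 = 234.
- For X ~ Bin(3000, 0.078): P(X ≥ 214) = 0.920, P(X ≥ 215) = 0.909, P(X ≥ 216) = 0.897. The stated 214 at 90% holds.
- Rare reaction: 1 − 0.999^3000 = 0.9503. The stated 95% holds.

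These figures anchor the size of the any-reaction endpoint. They do not bear on the gap itself.

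**Can the PT rows be added?** Take each row as a count of patients. One patient may have several terms, so the number of distinct patients lies between the largest row and the sum of rows. The documents give no subgroup sizes or counts. Assume four hepatic PT rows of 2, 2, 1 and 1 in liver-impaired patients: largest = 2, sum = 6.

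| Assumed subgroup size | If 2 patients (exact 95% CI) | If 6 patients (exact 95% CI) |
|---|---|---|
| 30 | 6.7% (0.8 to 22.1) | 20.0% (7.7 to 38.6) |
| 60 | 3.3% (0.4 to 11.5) | 10.0% (3.8 to 20.5) |
| 300 | 0.7% (0.1 to 2.4) | 2.0% (0.7 to 4.3) |

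The rows alone leave a threefold uncertainty (6/2) in the point estimate. If all terms sit in one SOC, the SOC row gives an upper bound, but it also counts patients with other terms in that class.

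**Does the any-reaction endpoint stand in for it?** Assume a specification rate s and a tripled rate in the subgroup, with the extra patients having no other reaction. The any-reaction proportion becomes 7.8% + 2s.

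| Assumed s | Patients in 3000 | Share of 234 | Any reaction in subgroup | Ratio | Grouped ratio |
|---|---|---|---|---|---|
| 0.1% | 3 | 1.3% | 8.0% | 8.0/7.8 = 1.03 | 3 |
| 0.5% | 15 | 6.4% | 8.8% | 8.8/7.8 = 1.13 | 3 |
| 1.0% | 30 | 12.8% | 9.8% | 9.8/7.8 = 1.26 | 3 |

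In expectation, the any-reaction ratio dilutes a threefold excess to between 1.03 and 1.26 over this range.

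**How much would the grouped row show?** The chance of seeing no patient at all in the subgroup is (1 − 3s)^n.

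- s = 0.1%: 0.997^60 = 0.83; 0.997^150 = 0.64.
- s = 0.5%: 0.985^60 = 0.40; 0.985^150 = 0.10.
- s = 1.0%: 0.970^60 = 0.16; 0.970^150 = 0.01.

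For 1% against 3% (two-sided 5%, normal approximation, rough at these counts), power is about 0.39 with 60 subgroup patients and 0.58 with 150. The row can describe; it cannot reliably detect.

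**The case against.** A reader might infer that hepatic reactions in liver-impaired patients, or bleeding with interacting drugs, are never counted per patient. The documents do not support that. Layer 3 of SAP 8.2.3.3 tabulates every reaction by SOC and PT within exactly those subgroups, SAP 8.2.3.1.5 counts patients with each listed specification overall, and the listings would allow a hand count. Nor can one say that the cells will hold only 0 or 1 patient: no cell counts are given, and SOC rows pool terms.

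Further points against:

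- The term lists are unseen. A specification might map to one PT or one SOC, and then the gap narrows or closes. One of the seven terms, rash, might also sit in a specification list.
- Protocol 13 names no subgroup criterion. Protocol 8.7 commits only to the number and proportion of patients with adverse reactions, so the SAP already exceeds it.
- Testing is exploratory (SAP 4), additional analyses are permitted, and the added row would often be too sparse to show even a threefold excess.

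All of this stands, and it limits the point to a missing summary. It does not remove it. A hand count from listings is not a planned analysis, and for coadministration it would need date matching because only events after the start of coadministration count. Sparse data call for a count with its interval, not for leaving the count out.

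**Conclusion.** The point holds in a limited form. No text commits to a grouped, one-count-per-patient analysis of any safety specification by subgroup; only SOC and PT rows without risk ratios are planned at that level. The size depends on the term lists. If a specification spans several PTs or SOCs, the distinct-patient count in a subgroup is not recoverable from the tables, and in the assumed example it could be off by a factor of three. The rates, row counts and subgroup sizes used here are assumptions, since the documents give none. Nothing planned is invalid or contradictory on this point. The absence of anaphylaxis from SAP 8.2.3.1.5 is a related mismatch with Protocol 7.1, to which SAP 2.1 itself refers. This is a low-priority but cheap improvement.

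**What to change.** In SAP 8.2.3.3, add one event row per safety specification in Protocol 7.1 to the existing tables by hepatic impairment, renal impairment, age, pregnancy and coadministration.

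- Use the separately specified event groups and count each patient once per specification.
- Include anaphylaxis, and add it to 8.2.3.1.5 and to the separate event definitions if it is not there.
- Label the hepatic event row so that it is not confused with the baseline factor; the SAP calls both hepatic impairment.
- Give number, proportion and the exact 95% interval of SAP 8.1.3. Give a risk ratio only under the existing rule for categories with less than 10 patients and where event counts allow, since that rule looks at category size and not at events.
- State that the rows are descriptive.

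The cost is SAP wording and a few rows in an existing table program. No new data, sample size or clinical rule is touched. The price in interpretation is wide intervals and many sparse cells.
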